8. SOFTWARE

All analyses will be done using SAS Version 9.4 or higher.

10. APPENDIX

10.1. Summary of Statistical Analyses

Primary Efficacy Analysis:

Endpoint	Analysis Populations	Estimand	Statistical Method	Supportive Analysis	Subgroup Analysis	Other Analyses
Primary Endpoint						
Percent change from baseline in calculated LDL-C at week 16	ITT	ITT estimand: The calculated LDL-C at week 16 will be the LDL-C value obtained within the week 16 efficacy analysis window, regardless of adherence to treatment and subsequent therapies.	MMRM	Yes	Yes	
 1. mITT 2. PMM (randomized population) 3. MMRM using strata based on observed data

10.2. Windows for Analysis Time Points

Below are the definitions for the visit windows programmatically imposed on measures repeatedly collected over the course of the study. These visit windows reflect the study schedule of assessments as described in the protocol.

The visit windows are constructed using ranges applied to the number of days in study (study days) when the measure is collected. Below are the relevant definitions for the analysis visit windows:

1. Study day is defined as the number of days since the first study treatment administration +1. The first study treatment occurs on Study Day 1.
2. Open-label study day is defined as the number of days since the first open-label study treatment administration+1
3. Since the protocol specifies that measurements be collected before study treatment is administered on a given day, it is appropriate that baseline include Day 1.
4. For randomized but not treated patients, Day 1 is the day of randomization.

Table 1 Global Analysis Windows for Group B (IV)

Visit label	Targeted Study Day	Targeted Open-Label Study Day	Analysis Window in Study Day
Screening	< Day 1	N/A	Measurement obtained prior to first study treatment, and not defined as baseline visit
Baseline	1	N/A	Measurement obtained closest to first study treatment, while remaining prior to first study treatment
Week 2	15	N/A	2 to 21
Week 4	29	N/A	22 to 35
Week 6	43	N/A	36 to 49
Week 8	57	N/A	50 to 70
Week 12	85	N/A	71 to 98
Week 16	113	N/A	99 to 128
Week 20	141	N/A	129 to 154
Week 24	169	Day 1	155 to 182
Week 28	197	29	183 to 210
Week 32	225	57	211 to 238
Week 36	253	85	239 to 266
Week 40	281	113	267 to 294
Week 44	309	141	295 to 322

Visit label	Targeted Study Day	Targeted Open-Label Study Day	Analysis Window in Study Day
Week 48	337	169	323 to 350
Week 52	365	197	351 to 378
Week 56	393	225	379 to 406
Week 60	421	253	407 to 434
Week 64	449	281	435 to 462
Week 68	477	309	463 to 490
Week 72	505	337	491 to 518
FU – W4	For patients prematurely discontinued trt: last study trt + 28 days For patients completed OLTP: 533	For patients prematurely discontinued trt: last study trt + 28 days For patients completed OLTP: 365	For patients prematurely discontinued trt: last study trt to 56 days after last study trt For patients completed OLTP: 519 to 560
FU – W12	For patients prematurely discontinued trt: last study trt + 84 days For patients completed OLTP: 589	For patients prematurely discontinued trt: last study trt + 84 days For patients completed OLTP: 421	For patients prematurely discontinued trt: 57 days after to 112 days after last study trt For patients completed OLTP: 561 to 616
FU – W20	For patients prematurely discontinued trt: last study trt + 140 days For patients completed OLTP: 645	For patients prematurely discontinued trt: last study trt + 140 days For patients completed OLTP: 477	For patients prematurely discontinued trt: 113 days after to 168 days after last study trt For patients completed OLTP: 617 to 672
FU > W20	N/A	N/A	For patients prematurely discontinued trt: >168 days after last study trt For patients completed OLTP: > 672

Study days are calculated from the day of first double-blind IMP infusion, the day of first double-blind IMP infusion being Day 1. For randomized but not treated patients, Day 1 is the day of randomization.

Table 2 Efficacy Analysis Windows – Statistical Testing for Group B (IV)

Visit Label	Targeted study day	Analysis window in study days
Screening	< Day 1	Measurement obtained prior to first study treatment, and not defined as baseline visit
Baseline	1	Measurement obtained closest to first study treatment, while remaining prior to first study treatment
Week 2	15	2 to 21
Week 4	29	22 to 35
Week 6	43	36 to 49
Week 8	57	50to 70
Week 12	85	71 to 98
Week 16	113	99 to 128
Week 20	141	129 to 154
Week 24	169	155 to 182

Table 3 Global Analysis Windows for Group A (SC)

Visit label	Targeted Study Day	Analysis Window in Study Day
Screening	< Day 1	Measurement obtained prior to first study treatment, and not defined as baseline visit
Baseline	1	Measurement obtained closest to first study treatment, while remaining prior to first study treatment
Week 1	8	2 to 11
Week 2	15	12 to 18
Week 3	22	19 to 25
Week 4	29	26 to 32
Week 5	36	33 to 39
Week 6	43	40 to 46
Week 7	50	47 to 53
Week 8	57	54 to 60
Week 9	64	61 to 67
Week 10	71	68 to 74
Week 11	78	75 to 81
Week 12	85	82 to 88
Week 13	92	89 to 95

Visit label	Targeted Study Day	Analysis Window in Study Day
Week 14	99	96 to 102
Week 15	106	103 to 109
Week 16	113	110 to 140
FU – W8	For patients prematurely discontinued trt: last study trt + 56 days For patients completed DBTP: 169	For patients prematurely discontinued trt: last study trt to 84 days after last study trt For patients completed DBTP: 141 to 196
FU – W16	For patients prematurely discontinued trt: last study trt + 112 days For patients completed DBTP: 225	For patients prematurely discontinued trt: 85 days after last study trt to 137 days after last study trt For patients completed DBTP: 197 to 249
FU – W23	For patients prematurely discontinued trt: last study trt + 161 days For patients completed DBTP: 274	For patients prematurely discontinued trt: 138 days after last study trt to 186 days after last study trt For patients completed DBTP: 250 to 298
FU > W23	N/A	For patients prematurely discontinued trt: >186 days after last study trt For patients completed DBTP: > 298

Table 4 Efficacy Analysis Windows – Statistical Testing for Group A (SC)

Visit label	Targeted Study Day	Analysis Window in Study Day
Screening	< Day 1	Measurement obtained prior to first study treatment, and not defined as baseline visit
Baseline	1	Measurement obtained closest to first study treatment, while remaining prior to first study treatment
Week 2	15	12 to 21
Week 4	29	22 to 35
Week 6	43	36 to 49
Week 8	57	50 to 63
Week 10	71	64 to 77
Week 12	85	78 to 91
Week 14	99	92 to 106
Week 16	113	107 to 126

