Safety:															
Weight	X	X	X	X	X	X	X	X	X	X	X	X	X	X	X
Vital Signs ¹¹	X	X	X	X	X	X	X	X	X	X	X	X	X	X	X
Physical Examination									X						
Electrocardiogram ³									X						X
Contraception Use Reminder ¹	X	X	X	X	X	X	X	X	X	X	X	X	X	X	X
Remind male patients to use condoms	X	X	X	X	x	x	X	x	X	X	X	X	X	X	X
Adverse Events	X	X	X	X	X	X	X	X	X	X	X	X	X	X	X
Laboratory Testing²:															
Hematology	X	X	X		X	X	X	X	X	X	X	X	X	X	X
Chemistry	X	X	X		X	X	X	X	X	X	X	X	X	X	X
Urinalysis	X	X	X		X	X	X	X	X	X	X	X	X	X	X
Core Lipid Panel	X	X	X	X	X	X	X	X	X	X	X	X	X	X	X
Specialty Lipid Panel	X		X		X	X	X	X	X	X	X	X	X	X	X
HbA1c						X			X			X			X
hs-CRP	X					X			X			X			X
Pregnancy Test	U		U		U	U	U	U	U	U	U	U	U	U	U

	Double Blind Treatment Period									Open-Label Treatment Period					
	Visit 2	Visit 3	Visit 4	Visit 5	Visit 6	Visit 7	Visit 8	Visit 9	End of DBTP Visit 10	Visit 11	Visit 12	Visit 13	Visit 14	Visit 15	Visit 16
Day	1	15	29	43	57	85	113	141	169	197	225	253	281	309	337
Visit Window (Day)	±3	±3	±3	±3	±3	±3	±3	±3	±3	±3	±3	±3	±3	±3	±3
Week	0	2	4	6	8	12	16	20	24	28	32	36	40	44	48
PK and Research Samples:															
PK (evinacumab, alirocumab) ⁴ , ANGPTL3, and PCSK9	X	X	X	X	X		X		X			X			X
Anti-evinacumab antibody sample	X		X			X			X			X			X
Research samples (biomarkers)	X			X		X			X			X			X
LDL-R function sample ⁵	X														
████████████████████	X	X													
████████████████████	X														
Other:															
Review of low fat diet	X	X	X	X	X	X	X	X	X	X	X	X	X	X	X

Table 5: Schedule of Events for IV Treatment Group B (Continued for Open-Label)

	Open-Label Treatment Period - Continued (Group B)					
	Visit 17	Visit 18	Visit 19	Visit 20	Visit 21	End of Open-Label Visit 22
Day	365	398	421	449	477	505
Visit Window (Day)	±3	±3	±3	±3	±3	±3
Week	52	56	60	64	68	72
Treatment:						
Administer Open-Label IV Study Drug ^{4,7}	X	X	X	X	X	
Concomitant Medications	X	X	X	X	X	X
Query LMT compliance	X	X	X	X	X	X
Safety:						
Weight	X	X	X	X	X	X
Vital Signs ¹¹	X	X	X	X	X	X
Contraception Use Reminder ¹	X	X	X	X	X	X
Remind male patients to use condoms	X	X	X	X	X	X
Adverse Events	X	X	X	X	X	X
Laboratory Testing²:						
Hematology			X			X
Chemistry			X			X
Urinalysis			X			X
Core Lipid Panel	X	X	X	X	X	X
Specialty Lipid Panel			X			X
HbA1c			X			X
hs-CRP			X			X
Pregnancy Test	U	U	U	U	U	U
PK and Research Samples:						
PK (evinacumab, alirocumab) ⁴ , ANGPTL3, and PCSK9			X			X
Anti-evinacumab antibody sample			X			X
Research samples (biomarkers)			X			X
Other:						

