8.1.2. Early Termination Visit

Patients who withdraw or are withdrawn from the study before EOT visit

Patients who withdraw or are withdrawn from the study before the week 16 visit, will be asked to return to the clinic for 2 visits: once for an early termination/EOT visit, consisting of the EOT assessments described in [Table 3](#) and [Table 4](#), and again at the EOS visit. The EOT visit should take place within 5 days of treatment discontinuation, if possible. A final EOS visit should take place with assessments as specified in the EOS visit (ie, follow-up visit) at 24 weeks after the last dose of study drug ([Table 6](#) and [Table 7](#)).

Patients who withdraw or are withdrawn from the study after EOT Visit

Patients who are withdrawn from the study after the EOT visit (week 16 for SC group or week 24 for IV group) will be asked to return to the clinic for early termination assessments/EOS, only. The EOS visit should take place with assessments as specified in the EOS visit (ie, follow-up visit) at 24 weeks after the last dose of study drug.

Sexually active patients who discontinue the study prematurely should have an unscheduled visit to remind patients to maintain highly effective contraceptive measures for 24 weeks after the last dose of study drug. At this visit, WOCBP will be provided urine pregnancy tests with instructions to test for pregnancy Q4W until the EOS visit. All patients should also be notified of Q4W follow-up phone calls to confirm contraception use, remind them of pregnancy reporting, and to obtain the results of the urine pregnancy test.

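### Group B follow-up windows count from the last dose for early stoppers but from end of treatment for completers, so the early-stopper windows overlap regular visits and end on the end-of-study day itself

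*SAP*

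**What the plan says.** SAP 10.2 states that its visit windows follow the protocol's assessment schedule. For Group B, Table 1 (global windows, used for safety data) then gives each follow-up row two definitions.

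- FU-W4 target: "For patients prematurely discontinued trt: last study trt + 28 days For patients completed OLTP: 533". The early-stopper window runs from the last dose itself to 56 days after it; the completer window is study days 519 to 560.
- FU-W12 target: "For patients prematurely discontinued trt: last study trt + 84 days For patients completed OLTP: 589". Windows: 57 to 112 days after the last dose; study days 561 to 616.
- FU-W20 target: "For patients prematurely discontinued trt: last study trt + 140 days For patients completed OLTP: 645". Windows: "For patients prematurely discontinued trt: 113 days after to 168 days after last study trt"; "For patients completed OLTP: 617 to 672".
- FU > W20, which has no target day: "For patients prematurely discontinued trt: >168 days after last study trt"; after day 672 for completers.

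Protocol 6.3 and 8.1.2 place the end-of-study visit of patients who leave the study early "at 24 weeks after the last dose of study drug". Protocol 7.4.2 treats another group separately: patients who stop drug but stay in the study have an end-of-treatment type visit and then go back to the planned visit calendar. Protocol Table 7 allows ±7 days around scheduled Group B follow-up visits.

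**The concern.** The same label means a different time since last dose for the two types of patient. That has two practical effects.

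(a) Because FU-W4 for early stoppers starts on day 0, it covers days that SAP 5.8.3 and 5.8.4 count as treatment (up to last dose + 28 days), and it overlaps the study-day windows for the regular visits. SAP 6.4 says how to choose among several values in one window. It does not say what to do with one value that belongs to two windows. Two programmers could put the same on-treatment laboratory value in different rows.

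(b) FU-W20 for early stoppers ends on the day on which the protocol places the end-of-study visit of a withdrawing patient. A visit on the target day is inside; a visit one day later falls in an open-ended row. In the Group B follow-up schedule, weight, physical examination, ECG, hs-CRP and anti-drug antibody are collected only at end of study, so any follow-up display of them would be split across two rows.

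**Working it through.** **Inputs.** Open-label visit days, Protocol Table 5: "Day 365 398 421 449 477 505". The last infusion is at day 477 (week 68); day 505 (week 72) has no dose and is end of open label. Follow-up targets and windows are from SAP 10.2 Table 1. End of study at 24 weeks = 168 days after last dose is from Protocol 6.3 and 8.1.2.

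**Step 1: reproduce the plan's figure.** 477 + 168 = 645 and 505 + 140 = 645. Day 645 is the completers' FU-W20 target. For completers, then, the 20 weeks count from end of treatment.

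**Step 2: put both sets on one scale** (days after last dose; for completers, study day minus 477).

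| Row | Completer target | Completer window | Early-stopper target | Early-stopper window |
|---|---|---|---|---|
| FU-W4 | 533 − 477 = 56 | 42–83 | 28 | 0–56 |
| FU-W12 | 589 − 477 = 112 | 84–139 | 84 | 57–112 |
| FU-W20 | 645 − 477 = 168 | 140–195 | 140 | 113–168 |

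All three targets are 28 days nearer the last dose for early stoppers. The window edges are 27 days nearer, except the first lower edge (42 days).

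**Step 3: overlap.** As an illustration, take a patient whose last infusion is on day 253 (week 36) and who stays in the study.

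- The pre-dose sample on day 253 lies in the Week 36 window (239–266) and also on day 0 of FU-W4.
- The sample on day 281 lies in the Week 40 window (267–294). Since 281 − 253 = 28, it is also exactly on the FU-W4 target.
- Both are within last dose + 28 days, so both fall in the treatment period used for the laboratory and vital-sign summaries.
- If the FU label wins, both values compete for FU-W4. SAP 6.4 keeps the one nearest the target (day 281), and the day-253 value disappears from the Week 36 row.
- A completer's visit 28 days after the last dose is day 505. It lies in Week 72 (491–518) and carries no FU label.

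**Step 4: end-of-study visit of a withdrawing patient.** Assume that ±7 days applies: days 168 − 7 = 161 to 168 + 7 = 175, which is 15 days.

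- Even spread: 161–168 (8 days) fall in FU-W20; 169–175 (7 days) fall in FU > W20. 7/15 = 47%.
- Clustered on day 168 (normal, rounded to whole days, limited to 161–175): 31% outside with SD 1 day, 40% with SD 2, 43% with SD 3, 45% with SD 5.
- With any symmetric spread that puts some visits on day 168, the share outside is (1 − share on day 168)/2, so below 50%.

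**Step 5: comparators.** For completers, all 15 on-time days fall in 140–195. For Group A early stoppers the last window is 138–186 days, and again all 15 fall inside.

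**Step 6: patients who stop drug but keep the planned calendar.** Step 4 does not describe them. If the last infusion was on day 449 or earlier, day 645 is at least 645 − 449 = 196 days after it, so under the early-stopper rows their end-of-study visit is in FU > W20.

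**The case against.** The strongest reply is that most specified outputs never use these rows. By-visit laboratory and vital-sign summaries for Group B stop at last dose + 28 days, or at the first open-label dose for the double-blind period (SAP 5.8.3, 5.8.4). HbA1c, hs-CRP and HDL-C are summarised within the treatment period (SAP 5.9). ECG abnormalities and potentially clinically significant values (PCSV) are counted over the treatment-emergent period whatever the visit label (SAP 5.8, 5.8.5). Physical examination is a listing. Drug-concentration plots and antibody persistence use nominal or actual sampling times. Efficacy testing uses Table 2, which has no follow-up rows. This largely disposes of effect (b) for the specified summaries. What remains is that SAP 5.8 says the global windows serve assessments through follow-up, and SAP 7.3 plans a final safety analysis through follow-up, so follow-up displays may be produced. The reply does not reach effect (a), because days 0 to 28 are inside the treatment period.

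A second reply is that this is a convention. Group A uses the same anchoring, with an offset of one dosing interval (7 days), and 140 days is literally 20 weeks. Protocol 5.1.2 also has a sentence giving the IV follow-up as 20 weeks from the last dose. That may explain the +140. But the same section opens with 24 weeks after the last dose, equated with 20 weeks after end of treatment, and 6.3 and 8.1.2 give 24 weeks. These passages must be reconciled. In Group A the convention is harmless at the far end because the last window extends to day 186.

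A third reply is that day 168 is the end of the treatment-emergent period. That period is defined separately, and the completers' window runs to day 195, so the cut-off is not applied consistently.

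Finally, Protocol 6.3 and 8.1.2 state no allowance around the early-termination end-of-study visit; the ±7 days is borrowed from Table 7. That stands, and it makes the 47% conditional.

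**Conclusion.** The inconsistency is exact: same labels, targets 28 days apart, an early-stopper FU-W4 that starts on the last-dose day with no rule for double membership, and an FU-W20 that ends on the protocol's end-of-study day.

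A reader might go on to infer that about half of early stoppers' end-of-study data are lost, or that the planned laboratory and ECG summaries will mix different washout times. The documents support neither. Values after day 168 go to another row and still appear in the data. The specified by-visit summaries end before those days, and ECG is not summarised numerically by visit. The 7 of 15 applies only to patients who withdraw from the study, and only if ±7 days applies and visits spread evenly; with clustering on day 168 it is about 31–45%.

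The effect is confined to descriptive by-visit safety displays for a small number of Group B early stoppers. For scale, the sample-size section's 5% dropout applied to 108 patients gives 0.05 × 108 = 5.4. That is only indicative, because the rate was not set for drug discontinuation over the whole study. Efficacy testing, PCSV counts and ECG-abnormality counts are unaffected. This is a minor correction, but the rule as written is wrong and is easy to put right before programming.

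**What to change.** In SAP 10.2 Table 1, use one set of last-dose offsets for both types of Group B patient: FU-W4 42–83, FU-W12 84–139, FU-W20 140–195, and later than 195 days. All 15 on-time end-of-study days (161–175) then fall in FU-W20.

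Add a precedence rule to SAP 6.4: a value before day 42 after the last dose, or one taken at a regular visit that the patient still attends after stopping drug, keeps its study-day visit label. The rule would also serve Group A, whose FU-W8 row for early stoppers likewise opens on the last-dose day. State as well which row applies to patients who stop drug early and attend the Table 7 visits on the planned calendar, since day 645 can be 196 days or more after their last dose.

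The cost is an edit to one table and a sentence or two of text. No new data are needed, and SAP version 2 has already revised this same appendix.

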10.3. List of AESIs with Data Sources and Definitions of SMQ/CMQ

Table 3 Summary of AESIs and the Methods of Data Collections and Derivations

AESI	Using an e-CRF specific tick box on AE page	Using Standard MedDRA Query (SMQ)/company MedDRA Query (CMQ) or lab data
Anaphylactic reactions	Yes	No
General allergic events	No	SMQ “hypersensitivity” (broad and narrow) excluding the following preferred terms linked to local injection site reactions (“infusion site dermatitis”, “infusion site hypersensitivity”, “infusion site rash”, “infusion site urticaria”, “injection site dermatitis”, “injection site hypersensitivity”, “injection site rash”, “injection site urticaria”, “injection site vasculitis”) plus “idiopathic angioedema”
Infusion reactions	Yes	No
Hepatic Disorders	No	
 • SMQ Drug-related hepatic disorder • Potentially clinically significant value (PCSV) in Appendix 10.4, • Hy’s law eDISH plot,
Pregnancy	Yes	No
Symptomatic overdose with investigational medicinal product	Yes	No
Neurocognitive events	No	CMQ for neurocognitive events as define based on Regulatory Agency request for another lipid lowering program (See Table 4

AESI	Using an e-CRF specific tick box on AE page	Using Standard MedDRA Query (SMQ)/company MedDRA Query (CMQ) or lab data
		in Appendix 10.3 for the list of terms)
Neurologic events	Yes	No
New onset of diabetes (NOD)	No	
No medical history of diabetes as specified in “Cardiovascular History and Cardiovascular Risk Factors” CRF page
 
AND
 
one of the following criteria:
 
 • Lab criteria: At least 2 values of HbA1c $\geq 6.5\%$ during the TEAE period. NOTE: For patients with only a single measurement available during the TEAE period, a single value $\geq 6.5\%$ will be considered and qualify the patient as NOD by default. For patients with several HbA1c measurements but only with the last one $\geq 6.5\%$, this single value $\geq 6.5\%$ will be considered and qualify the patient as NOD by default. 
OR
 
 • Lab criteria: At least 2 values of fasting glucose ≥ 126 mg/dL (7.0 mmol/L). NOTE: For patients with only a single measurement available during the TEAE period, a single value ≥ 126 mg/dL (7.0 mmol/L) will NOT be considered and will NOT

AESI	Using an e-CRF specific tick box on AE page	Using Standard MedDRA Query (SMQ)/company MedDRA Query (CMQ) or lab data
		qualify the patient as NOD. For patients with several fasting glucose measurements but only with the last one ≥ 126 mg/dL (7.0 mmol/L), this single value ≥ 126 mg/dL (7.0 mmol/L) will NOT be considered and will NOT qualify the patient as NOD. OR 
 • HLT Diabetes mellitus (incl subtypes) OR 
 • Initiation of any new concomitant medication for hyperglycemia during the treatment period
Diabetes mellitus or diabetic complications	No	
 • HLGT “diabetes complications” (including PTs pertaining to the secondary SOC included in the HLGT), HLT “diabetes mellitus”, and HLT “carbohydrate tolerance analyses (incl diabetes)” excluding PTs “blood glucose decreased” and “Glycosylated haemoglobin decreased” and including the PTs “hyperglycaemia”, “Hyperglycaemic unconsciousness” and “Hyperglycaemic seizure” from the HLT "Hyperglyceamic conditions NEC"

AESI	Using an e-CRF specific tick box on AE page	Using Standard MedDRA Query (SMQ)/company MedDRA Query (CMQ) or lab data
		
 Changes in diabetic medication dosage (specifically increases in dosage) or initiation of additional diabetic medication
Pancreatitis	Yes	No
Cataracts	No	HLT Cataract conditions
Immune complex diseases	No	SMQ (Narrow) Systemic lupus erythematosus SMQ (Narrow) Vasculitis SMQ (Narrow) Guillain-Barre syndrome
Muscle events/CK elevation	No	
 Lab data analyses (e.g. PCSV) All preferred terms under system organ class (SOC): Musculoskeletal and connective tissue disorders Rhabdomyolysis/myopathy (Narrow SMQ)

Table 4 CMQ “Neurocognitive disorders – FDA’s recommendation”

MedDRA level	MedDRA Term Label
PTCD	Amnesia
PTCD	Amnesic disorder
PTCD	Anterograde Amnesia
PTCD	Behavioural and Psychiatric Symptoms of Dementia
PTCD	Change in sustained attention
LLTCD	Cognitive Deterioration
PTCD	Cognitive Disorder
LLTCD	Confusion
LLTCD	Confusion Aggravated
PTCD	Confusional State

MedDRA level	MedDRA Term Label
PTCD	Delirium
PTCD	Dementia
PTCD	Dementia Alzheimer's type
LLTCD	Dementia Nos
LLTCD	Dementia Nos Aggravated
LLTCD	Dementia of the Alzheimer's type NOS
PTCD	Dementia with Lewy Bodies
PTCD	Disorientation
PTCD	Disturbance in attention
PTCD	Executive dysfunction
PTCD	Frontotemporal Dementia
LLTCD	Global Amnesia
PTCD	Illogical Thinking
PTCD	Impaired reasoning
PTCD	Incoherent
PTCD	Judgement impaired
PTCD	Memory Impairment
PTCD	Mental Impairment
LLTCD	Mental Impairment Nos
LLTCD	Mental State Abnormal Aggravated
PTCD	Mental Status Changes
PTCD	Mini Mental Status Examination Abnormal
PTCD	Presenile Dementia
PTCD	Retrograde Amnesia
PTCD	Senile Dementia
LLTCD	Senile Dementia Nos
LLTCD	Short-term Memory Loss
PTCD	Thinking Abnormal
LLTCD	Thinking Slowed
PTCD	Transient Global Amnesia
PTCD	Vascular Dementia

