6.2.3. Exclusion Criteria

A patient who meets any of the following criteria will be excluded from the study:

1. Known history of homozygous FH (clinically, or by previous genotyping)
2. Use of any medication or nutraceutical (other than a statin or PCSK9 inhibitor antibody) known to alter serum lipids and which has not be stable for at least 4 weeks (6 weeks for fibrates) before screening.
3. Unwilling to maintain current exercise regimen and/or general physical activity level for the duration of the study
4. Presence of any clinically significant uncontrolled endocrine disease known to influence serum lipids or lipoproteins

Note: Patients on thyroid replacement therapy can be included if the dosage of the replacement therapy has been stable for at least 12 weeks prior to screening and the thyroid stimulating hormone (TSH) level is within the normal range of the central laboratory at the screening visit.

5. Use of thyroid medications (except for replacement therapy which has been stable for at least 12 weeks before screening)
6. Newly-diagnosed (within 3 months prior to screening visit) or poorly-controlled (hemoglobin A1c [HbA1c] > 9%) diabetes
7. Daily doses above atorvastatin 80 mg, rosuvastatin 40 mg, or simvastatin 40 mg (except for patients on simvastatin 80 mg for > 1 year)
8. Use of estrogen or testosterone therapy unless the regimen has been stable in the past 6 weeks prior to the screening visit and there are no plans to change the regimen during the study
9. Use of systemic corticosteroids, unless used as replacement therapy for pituitary/adrenal disease with a stable regimen for at least 6 weeks prior to randomization

Note: Topical, intra-articular, nasal, inhaled and ophthalmic steroid therapies are not considered as 'systemic' and are allowed.

10. Initiation of a new diet or major change to a previous diet within 4 weeks prior to screening
11. Conditions/situations such as:
- Any clinically significant abnormality identified at the time of screening that, in the judgment of the investigator or any sub-investigator, would preclude safe completion of the study or constrain endpoints assessment; eg, major systemic diseases, patients with short life expectancy
 - Considered by the investigator or any sub-investigator as inappropriate for this study for any reason, eg:
 - Deemed unable to meet specific protocol requirements, such as scheduled visits
 - Deemed unable to tolerate injections, as per the patient or the investigator

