4. ANALYSIS VARIABLES

4.1. Demographic and Baseline Characteristics

For each patient, demographic and baseline characteristics will be obtained from the last available value up to the date of the first study treatment administration (i.e. baseline definition). For patients randomized and not treated in R1500-CL-1643, the baseline value is defined as the last available measurement prior to the date of randomization.

All baseline safety and efficacy parameters (apart from those listed below) will be presented along with the summary statistics in the safety and efficacy sections.

The following variables will be summarized:

Demographic Characteristics

- Sex (Male, Female)
- Race (White, Black or African American, Asian, American Indian or Alaska Native, Native Hawaiian or other Pacific Islander, Not Reported, Other)
- Age in years (quantitative and qualitative variable: ≥ 18 to < 45 , ≥ 45 to < 65 , ≥ 65 to < 75 , and ≥ 75 years; and < 65 , and ≥ 65 years)
- Ethnicity (Hispanic or Latino, Not Hispanic or Latino, Not reported, Unknown)

Baseline Characteristics

- Baseline Weight (kg)
- Baseline Height (cm)
- Baseline Body mass index (BMI) in kg/m^2 (quantitative and qualitative variable defined as < 30 , ≥ 30)
- Smoking Status (never, former, and current smoker)
- Current alcohol consumption (yes/no)
- Randomization strata as reported in the IVRS
 - High intensity statin (Yes/No)
 - HeFH status (Yes/ No)
- Randomization strata as reported from the e-CRF

Baseline Disease Characteristics

- Lipid parameters - quantitative variables for all efficacy parameters

- HbA1c both quantitative variable and qualitative variable defined as: <5.7%, ≥5.7% to <6.5%, ≥6.5%
- hs-CRP
- Calculated LDL-C categories: <70, ≥ 70 to <100, ≥100 to <130, ≥130 to <160, ≥160 to <190, ≥190 mg/dL (<1.81, ≥1.81, <2.59, ≥2.59 to <3.37, ≥3.37 to <4.14, ≥4.14 to <4.91, ≥4.91 mmol/L)
- Fasting TG categories: <150, ≥150 to <200, ≥200 mg/dL, and category ≥150 mg/dL for mixed dyslipidemia (<1.7, ≥1.7 to <2.3, ≥2.3 mmol/L, and category ≥ 1.7 mmol/L),
- Lp(a) categories: <30, ≥30 to <50, ≥50 mg/dL, and category ≥30 mg/dL (<75, ≥75 to <125, and ≥125 nmol/L, and category ≥ 75 nmol/L)

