4.8.1. Adverse Events Variables

The period of safety observation starts from the time when the patient gives informed consent and continues into the following periods:

- The PRE-TREATMENT period is defined from the day the ICF is signed to the day before the first dose of double-blind study treatment administration.
- The double-blind treatment-emergent adverse event (TEAE) period is defined from the day of the first dose of double-blind study treatment administration to the day of the last dose of double-blind study treatment administration + 168 days (24 weeks) (based on PK considerations, residual effect of study treatment might be observed until 24 weeks after the last dose of study drug) for those patients not proceeding into the OLTP (ie, Group A patients and Group B patients who prematurely discontinue study treatment), or up to the day before the first dose of open-label study treatment administration for those patients proceeding into the OLTP
- The open-label treatment-emergent adverse event (TEAE) period (Group B only) is defined from the day of the first open-label study treatment administration to the day of the last open-label study treatment administration + 168 days (24 weeks).
- The POST-TREATMENT period is defined from the day after the end of the respective TEAE periods to the last study visit.

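### The new-onset diabetes rule checks recorded history but not baseline HbA1c, so unrecorded diabetes present at entry can be counted as a new case

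*SAP*

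**What the plan says.** SAP Appendix 10.3 makes a patient a new-onset case when two things hold. The first is "No medical history of diabetes as specified in" the cardiovascular history and risk factor CRF page. The second is any one of four criteria: HbA1c of at least 6.5%, fasting glucose of at least 126 mg/dL, a term in the diabetes mellitus HLT, or a newly started drug for high blood glucose.

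- **HbA1c.** Two values in the TEAE period are needed, with two defaults. One begins "For patients with only a single measurement available during the TEAE period, a single value" and goes on to count that value if it is 6.5% or more. The other counts a patient whose last value alone is that high.
- **Glucose.** The criterion is "At least 2 values of fasting glucose" at or above 126 mg/dL. A single high value expressly does not count.
- **Eligibility.** Protocol 6.2.3, criterion 6, excludes "Newly-diagnosed (within 3 months prior to screening visit) or poorly-controlled (hemoglobin A1c [HbA1c] > 9%) diabetes".
- **Baseline data.** SAP 4.1 lists "HbA1c both quantitative variable and qualitative variable defined as" three categories, the top one being 6.5% or more.

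The definition in Protocol 9.4.3 has neither a history condition nor a baseline laboratory condition.

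**The concern.** The history condition shows that the SAP means to separate new disease from existing disease, but it catches only disease that someone has written down. No laboratory criterion asks for a baseline below the threshold or for a change from baseline. A patient with unrecorded diabetes at entry can therefore be reported as having developed it on study drug.

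At stake is the incidence of an adverse event of special interest. Counting existing cases raises the rate in every arm and pulls the evinacumab-to-placebo ratio toward 1. With 36 patients per arm, a chance imbalance of a few such cases could also create or hide an apparent signal. The open-label period has no control arm against which the inflation would show.

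The SAP already conditions on baseline for similar measures: in Appendix 10.4 the ALT, AST, alkaline phosphatase, bilirubin and CPK criteria all require a baseline at or below the cutoff.

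**Working it through.** No sample size, power or alpha figure depends on this rule, so there is no plan figure to reproduce. The check sets the rule against eligibility and the visit schedule, then illustrates the scale.

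**1. Can such a patient enter?** Criterion 6 removes diabetes diagnosed within 3 months before screening, and HbA1c above 9%. An undiagnosed patient with HbA1c of 6.5% to 9% passes it.

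**2. Which scheduled HbA1c values fall in the double-blind TEAE period?** SAP 4.8.1 says the period "is defined from the day of the first dose of double-blind study treatment administration". It ends 168 days after the last double-blind dose or, in Group B, "up to the day before the first dose of open-label study treatment administration for those patients proceeding into the OLTP".

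- Group A (Protocol Tables 3 and 6): the last dose is on day 106, so the period ends on day 106 + 168 = 274. Values on days 113, 169, 225 and 274 fall inside it.
- Group B patients entering open label (Protocol Table 4): the first open-label dose is on day 169, so the period ends on day 168. HbA1c is scheduled on days 85 and 169; only day 85 falls inside.

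On schedule, these Group B patients have exactly one measurement, so the single-measurement default applies. One week 12 value of 6.5% or more makes a case, even if screening HbA1c was the same or higher.

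**3. Glucose.** Group B has six scheduled post-dose chemistry samples in the period (days 15, 29, 57, 85, 113, 141). The Day 1 pre-dose sample also carries a date inside the period. The criterion does not say post-baseline, so that pre-treatment value could be one of the two that qualify.

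**4. Scale (assumed inputs).** Let u be the share of patients with baseline HbA1c of 6.5% or more, no recorded diabetes, and values that stay above threshold. The documents do not give u. Expected false cases are 108u in Group B and 144u in Group A. For the ratio, assume true new-onset rates p of 2% on placebo and 6% on evinacumab (true ratio 3.0), with observed rate = u + (1 − u)p.

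| u | Group B false cases | Group A false cases | Observed placebo | Observed evinacumab | Observed ratio |
|---|---|---|---|---|---|
| 1% | 1.1 | 1.4 | 2.98% | 6.94% | 2.33 |
| 2% | 2.2 | 2.9 | 3.96% | 7.88% | 1.99 |
| 5% | 5.4 | 7.2 | 6.90% | 10.70% | 1.55 |

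For example, at u = 2%: 0.02 + 0.98 × 0.02 = 0.0396 and 0.02 + 0.98 × 0.06 = 0.0788; 0.0788 / 0.0396 = 1.99.

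**5. Chance imbalance.** With 72 evinacumab and 36 placebo patients in Group B, the probability that none of k false cases is on placebo is about (2/3)^k: 44% for k = 2 and 20% for k = 4.

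**The case against.** A reader might infer that everyone above a threshold at baseline becomes a new case. The rule does not say that. The patient must have no recorded diabetes and must also meet a criterion on study; someone whose values fall below threshold is not counted by the laboratory criteria.

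The route in is also narrower than criterion 6 alone suggests. HbA1c is measured at screening, and at pre-screening for run-in patients. Investigators must review laboratory values (Protocol 8.2.3.4), and a site could record diabetes or exclude the patient. This stands as mitigation, but neither document requires the site to record the diagnosis.

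Other displays help. Baseline HbA1c categories are tabulated by arm, so imbalance at entry would be visible. The fasting hyperglycaemia PCSV of 7 mmol/L is the same threshold as 126 mg/dL, and SAP 5.8.3 already splits it by baseline status, so the glucose side is partly covered. The HbA1c side is less so: its PCSV is above 8%, and SAP 5.9 plans no baseline split for it. None of these displays corrects the new-onset count.

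Safety summaries are descriptive and pool evinacumab regimens within route (SAP 5.8), giving 72 v 36 and 108 v 36. Under 2:1 pooling, two cases against none is unremarkable. That stands, and it limits the weight of the point.

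Finally, over-counting might be called conservative, like the SAP's handling of partial AE dates. That convention deals with missing information. Here the screening value is known, and counting existing cases weakens a comparison.

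**Conclusion.** The concern holds for HbA1c: followed exactly, the rule can count existing, unrecorded disease as new onset, most easily in Group B patients entering open label, where one week 12 value suffices.

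The size is unknown from the documents. About 1 to 5 false cases per 108 Group B patients follows only if 1% to 5% of patients enter above threshold without recorded diabetes and stay there. The diluted ratios rest further on the assumed 2% and 6% rates.

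A reader might infer a bias against evinacumab, or an effect on the trial's main conclusions. The documents support neither. Randomisation balances such patients on average, so the expected effect is a higher rate in every arm and a ratio closer to 1, apart from chance imbalance. No efficacy result, significance level or power figure is touched. The change is worth making because the count is wrong as defined and the data to correct it are already collected.

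**What to change.** In SAP Appendix 10.3:

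- Apply the HbA1c criterion only to patients with baseline HbA1c below 6.5%, and state how a missing baseline is handled.
- Count only post-baseline HbA1c and fasting glucose values.
- Remove patients with baseline HbA1c of 6.5% or more and no recorded history from the new-onset numerator and denominator, whichever criterion they later meet. List them separately as prevalent at entry.
- Do not exclude on one baseline fasting glucose of 126 mg/dL or more. The SAP itself holds that a single such value does not establish diabetes, and excluding on it could hide true cases. Flag glucose-defined cases, or present them, by baseline glucose status.

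Record the change in SAP 1.2.3 as a departure from the definition in Protocol 9.4.3. That section does not list the existing history condition either, so both can be entered together.

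The cost is a few sentences, one extra listing and a slightly smaller at-risk set. No new data are needed.
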